2.6 EXCLUSION CRITERIA AT STUDY ENTRY

1. Not fluent in Russian
2. Cognitive impairment resulting in inability to provide informed consent based on research assessor (RA) assessment
3. Known active TB or current febrile illness
4. Breastfeeding
5. Known uncontrolled psychiatric illness (such as active psychosis)
6. History of hypersensitivity to naltrexone, nalmefene, or naloxone
7. Current use (past week) of illicit or prescribed opiates as documented by either self-report or positive urine drug test
8. Unwilling to abstain from opiates during the treatment period
9. Current use of neuroleptics
10. History of seizure disorder
11. Known liver failure
12. ALT/AST levels >5x normal
13. History of Raynaud's disease
14. Planned surgeries in the next 3 months
15. Enrolled in another HIV and/or substance use medication intervention study
16. Taking naltrexone in the past 30 days
17. Taking nalmefene in the past 30 days

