Medication inserts will be provided to participants at baseline.

Medication distribution will be as follows:

Naltrexone:

- 28 capsules/bottle

- Participants will receive 1 bottle of 28 capsules at baseline and week 2.

Nalmefene:

- 28 capsules/bottle
- Participants will receive 1 bottle of 28 capsules at baseline and week 2.

Medication bottles will also be labeled. The medication labels will contain the following information:

FOR CLINICAL TRIAL USE ONLY

NALTREXONE/NALMEFENE

STORAGE: Don't store medication above 25°C.

KEEP OUT OF REACH OF CHILDREN AND PETS.

Return all unused medication to the study site.

DATE OF MANUFACTURE:

SHELF LIFE:

3.4.D. LOST OR STOLEN STUDY MEDICATION

If participants report lost or stolen medication, they will be provided with extra study medication. If participants report losing medication more than once, the study team will be alerted and the case discussed to determine a plan of action.

3.4.E. DISCONTINUATION OF STUDY MEDICATION

If as a result of study testing at week 4, a participant is found to have AST/ALT >10x normal, medications will be discontinued and the participants will be appropriately monitored for resolution of the abnormalities. If a participant has AST/ALT >5x normal as a result of study testing at week 4, participant will be rechecked at their 6-week visit to ensure levels do not increase to the threshold of discontinuation. Any participant with symptoms of acute hepatic failure (jaundice, dark urine) will have AST/ALT checked.

Those who discontinue medication will be followed and analyzed by intention to treat.

Participants found to be pregnant during the study will have their study medication discontinued, but will still be followed-up for the duration of the study. Participants who report pregnancy outside of study visits will be instructed to immediately discontinue their study medication and requested to come in for a confirmatory urine pregnancy test.

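### The plan omits a week-8 pregnancy test on urine it already collects and does not follow an on-study pregnancy to its outcome; a related week-8 liver point is minor

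*Combined protocol and SAP*

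**What the plan says.** **Pregnancy.** Section 2.5 requires a negative test and willingness to use adequate birth control at entry. The schedule in Section 3.5 marks pregnancy tests at screening, baseline and weeks 2, 4 and 6, and none at week 8. Section 3.6.B states the week-8 exception outright. The visit flow in Section 4.4 limits the pregnancy check at the two later full visits to week 4, while urine is still taken at week 8 for the adherence check. Section 3.6.B gives the reason for excluding pregnant women: reports of possible adverse events with the study drugs. Under Section 3.4.E, participants found pregnant "will have their study medication discontinued, but will still be followed-up for the duration of the study". The same section adds: "Participants who report pregnancy outside of study visits will be instructed to immediately discontinue their study medication". Section 6.1 lists a congenital anomaly or birth defect among the criteria for a serious adverse event.

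**Liver.** Section 3.4.E has two numerical rules, both tied to week-4 results. The first is "If as a result of study testing at week 4, a participant is found to have AST/ALT >10x normal, medications will be discontinued", after which "the participants will be appropriately monitored for resolution of the abnormalities". The second, for lower values, is "AST/ALT >5x normal as a result of study testing at week 4, participant will be rechecked at their 6-week visit", and the sentence goes on to give its aim: to make sure the level does not climb to the stopping threshold. A separate rule has no week limit: "Any participant with symptoms of acute hepatic failure (jaundice, dark urine) will have AST/ALT checked". AST/ALT is tested routinely at screening and weeks 4 and 8, and at week 6 only if the week-4 result calls for it (Section 3.6.C).

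**The concern.** Safety is one of the study's stated aims, and the protocol treats fetal exposure as a hazard serious enough to exclude pregnant women and to test them repeatedly. The testing nevertheless stops about two weeks before treatment does, and the final visit does not use a sample that is already in hand. A conception in the later part of treatment could go unrecognised by the study unless the participant reports it.

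For a pregnancy that is recognised, follow-up is promised only for the length of the study. With an 8-week course and no visit scheduled after week 8, that will normally be long before a birth. A birth defect would count as serious if it came to notice, but the plan has no active way for it to come to notice.

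The liver question looks similar at first: a raised value first seen at week 8 meets no numerical rule, and no scheduled visit follows.

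**Working it through.** The plan gives no figure on this point, so the size has to come from its dosing and visit-window rules.

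**Inputs**
- Dosing: one capsule daily, starting on the baseline day (Sections 3.3, 3.3.A, 3.3.B). Two bottles of 28 give 56 capsules (Section 3.4.C). If none is missed, doses fall on day 0 to day 55.
- Week-6 visit, the last scheduled pregnancy test: target day 42, window day 35 to day 48 (Section 3.5.A).
- Week-8 visit: target day 56, window day 49 to day 62 (Section 3.5.A).
- Bottle label: "Return all unused medication to the study site". An early week-8 visit could therefore end dosing.

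**Doses after the last pregnancy test, all 56 capsules taken** (55 minus the test day)
- On target: 55 − 42 = 13, and 13/56 = 23%.
- Latest week-6 visit: 55 − 48 = 7, and 7/56 = 12.5%.
- Earliest week-6 visit: 55 − 35 = 20, and 20/56 = 36%.

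**Doses after the last test if a day-49 visit ends dosing** (last dose on day 48)
- Week-6 test on target: 48 − 42 = 6.
- Week-6 test on day 48: 48 − 48 = 0.

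The smallest possible count is therefore 0, not 7.

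**Time from the last test to the week-8 urine sample**
- On target: 56 − 42 = 14 days.
- Shortest: 49 − 48 = 1 day. Longest: 62 − 35 = 27 days.

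**Number of people.** At most 16 are randomized. Section 3.3 closes arm A to enrollment and sets arm B's target at 8. The number of women is not given, so 16 strips is a ceiling.

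**Liver: the provisions that do reach a week-8 result**
- Any value above the upper limit of normal is evaluated as a possible adverse event (Section 2.2).
- The participant is told of an abnormal result and advised to see a local provider (Section 6.2).
- An event discovered outside a visit is still recorded (Section 6.2).
- A follow-up plan is set case by case, ending at resolution, stabilization or the end of participation (Sections 6.3.B and 6.4).
- If the rise is judged serious, the site must keep seeking information until it resolves or stabilizes, or the participant is lost and terminated from the study (Section 6.3.C).
- Symptoms of acute liver failure trigger a test at any time (Section 3.4.E).

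What is left is a rise that is asymptomatic and judged non-serious. For that, a repeat test is at the investigators' discretion.

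**The case against.** The best defence on pregnancy is that the omission is deliberate. Three sections agree on it, so it is not a slip or a contradiction. Each scheduled test comes before further dosing, and a week-8 test would not, because treatment is ending. Contraception is required, self-reported pregnancy is covered, and participants are still asked about symptoms at week 8. This shows that the test has no role in dosing and that events should be few. It does not give a final check on exposure, and it does not supply an outcome for a pregnancy already found.

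A reader might infer that late pregnancies go unsought altogether. The documents do not support that: the week-6 test can fall as late as day 48, and under some visit timings no dose follows it.

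A reader might also infer that week-8 liver rises are unattended, or that treating a value above five times normal differently at weeks 4 and 8 is inconsistent. Neither follows. The week-4 recheck exists to protect the stopping threshold, and that purpose lapses when treatment ends. The general adverse-event provisions cover the rest, and a mandatory repeat at five times normal would mostly replace clinical judgment with a reviewer's preference.

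Nor does a week-8 value above five times normal show drug injury merely because entry excludes "ALT/AST levels >5x normal". Section 4.2 accepts an outside result up to 4 weeks old at screening, and Section 3.5.A allows baseline up to 28 days after screening. The qualifying value can therefore be about 28 + 28 = 56 days older than the first dose, in a population where Section 2.2 expects raised starting levels.

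**Conclusion.** The pregnancy point holds. Followed exactly, the plan leaves exposure after the week-6 test unchecked and does not actively seek the outcome of an on-study pregnancy. The untested stretch is 13 of 56 doses on target dates, 7 to 20 across the week-6 window with full dosing, and as few as 0 if an early final visit ends treatment. These counts measure the span of untested exposure. They do not say how many pregnancies a test would find, which the documents do not allow one to estimate. Expected frequency is low, and neither the primary outcome nor its analysis is affected. The change is worth making because it is cheap and protects participants.

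The liver point is minor and optional. The one piece worth carrying over is the duty to monitor for resolution when a value exceeds ten times normal, since that duty has a purpose beyond stopping the drug.

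This rests on two assumptions: that participation ends at or soon after week 8, because no later visit is scheduled and the end of participation is not defined; and, for the main dose counts, that no capsule is missed. Figures in Sections 6.3.C and 6.4 and the consent pages are not available, so terms for contact after the study cannot be judged.

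**What to change.** 1. Add a urine pregnancy test at week 8, run on the sample already collected for riboflavin, and amend Sections 3.5, 3.6.B and 4.4 to match.
2. In Sections 3.4.E and 3.6.B, replace follow-up limited to the study's duration with telephone follow-up of any on-study pregnancy to its outcome.
3. Optional: apply the existing monitoring for resolution above ten times normal to week-8 results as well. Leave the five-times recheck rule as it is.

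The cost of the first two is at most 16 strips, a few telephone calls, an amendment, possibly consent wording for contact after week 8, and later closure for any pregnancy followed. Participants already supply several alternative contacts (Section 4.7), so calls are feasible. The optional liver change could add a few blood tests. The week-8 strip would not alter dosing and may miss a very recent conception, so it narrows the gap without closing it.

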3.5 SCHEDULE OF DATA COLLECTION

		Screen	Baseline Visit	2 week visit	4 week visit	6 week visit	8 week visit
Screening	Screening Questions	X					
	Verification of HIV, non-pregnancy, urine tox, and ALT/AST	X					
Enrollment	Sign Informed Consent	X					
	Complete contact information/verify numbers	X					
	Randomization		X				
Laboratory	Clinical Values		X		X		X
	Pregnancy Test	X	X	X	X	X	
	Urine Drug Test	X	X				
	AST, ALT	X			X	X (if indicated)	X
	Cold Pressor Test		X		X		X
	Naloxone Challenge		X				
Assessment	Full Study Assessment		X		X		X
	Short Assessment			X		X	
Intervention	Symptom Management/Adverse Events		X	X	X	X	X
	Provide Medication Instructions		X				
	Give Study Medication		X	X			
	Discuss Adherence		X	X	X	X	
	Assess Adherence			X	X	X	X
Other	Provide Resource Card		X				
	Compensate for Participation	X	X	X	X	X	X
	Report Adverse Events		X	X	X	X	X
	Complete Tracking Forms	X	X	X	X	X	X

3.5.A. VISIT WINDOWS

Baseline Visit

- Window open: 1 day post screening
- Target date: 3 days post screening
- Window close: 28 days post screening
- Window length: 27 days

2 Week Visit

- Window open: 7 days post baseline
- Target date: 14 days post baseline
- Window close: 20 days post baseline

- Window length: 13 days

4 Week Visit

- Window open: 21 days post baseline
- Target date: 28 days post baseline
- Window close: 34 days post baseline
- Window length: 13 days

6 Week Visit

- Window open: 35 days post baseline
- Target date: 42 days post baseline
- Window close: 48 days post baseline
- Window length: 13 days

8 Week Visit

- Window open: 49 days post baseline
- Target date: 56 days post baseline
- Window close: 62 days post baseline
- Window length: 13 days

3.6 DATA SOURCES

3.6.A QUESTIONNAIRES

Questionnaires will be administered at baseline, 2-, 4-, 6-, and 8-week study visits. At weeks 4 and 8, assessments of tolerability of medication, medication discontinuation, treatment side effects, self-reported adherence, and self-reported pain will occur. At weeks 2 and 6, brief assessment of tolerability, side effects, and adherence will occur.

3.6.B. URINE

A pregnancy test will be administered by trained clinical research staff at screening to determine eligibility and at each study visit (except for 8-weeks).

Pregnant women will be excluded from the study due to some reports suggesting possible adverse events with study medications. Participants found to be pregnant will discontinue their study medication but will still be followed-up for the duration of the study.

Urine will also be checked at screening and baseline, as part of the naloxone challenge, to ensure that participants have not recently used opiates (as opioid receptor antagonists would be contraindicated as they could precipitate withdrawal). The urine drug test will test for a range of opioids, specifically opiates (products of the poppy plant – morphine, heroin) and synthetic opioids (specifically methadone).

If new opioids appear on the scene in Russia, such as fentanyl, then we will begin testing for this, but currently that is not thought to be an issue.

A urine sample will be collected from all participants at each study visit post-baseline while on study medication to be inspected for the presence or absence of Riboflavin, as a measure of medication adherence, as described in section 3.4b Adherence.

3.6.C. BLOOD

Blood will be collected at screening, 4- and 8-week study visits to assess AST/ALT levels. Blood may also be collected at the 6-week study visit for liver function testing, if indicated at the participant's 4-week study visit (see Section 3.4E).

3.6.D. COLD-PRESSOR TESTING

The cold-pressor test (CPT) is an experimental model that assesses cold pain threshold and tolerance. It is a research paradigm that has been used by researchers for decades, and has been utilized to measure enhanced sensitivity to cold pain (hyperalgesia). The investigators will use an automatic cooling water bath that keeps a constant temperature of 0-2 degrees Celsius. Participants are instructed to place their dominant arm in the cold water bath so that ice water covers the hand and approximately 10 cm of the forearm, to verbally indicate when they first perceive pain and, to rate their pain on a scale of 0-100 at its very worse, and when they can no longer tolerate the ice bath, to remove their arm from the water. The time from submersion to those events will be measured using a stopwatch. Cold pain threshold is measured as number of seconds to the initial perception of pain, and cold pain tolerance is measured as seconds until withdrawal of hand. Trials will be discontinued at 3 minutes since after this time pain severity diminishes as numbness sets in. This data will be collected at baseline, week 4 and week 8. Participants will be requested to refrain from over the counter analgesic use (non-steroidal anti-inflammatory pain medications or acetaminophen) for 24 hours prior to the study visit.

3.6.E. DAILY PAIN DIARY

Participants will be asked to keep a daily written record ("daily diary") of pain severity, medication adherence, and alcohol use. Although the daily diary responses may more accurately measure changes in pain compared to monthly assessments (which are subject to recall bias), it is uncertain whether this sample of participants will be able to comply with the request to record daily measurements. This study will test the feasibility of capturing data in this fashion.

4. STUDY PROCEDURES

4.1 RECRUITMENT

Existing Russia ARCH, who have agreed to be contacted for future studies, will be screened for the study. St PETER participants will also be screened for the study at their final St PETER study visit. Recruitment beyond the Russia ARCH cohort will occur at local NGOs and Russia ARCH network hospitals including the major clinical HIV hospitals (Botkin Infectious Disease Hospital, Leningrad Regional AIDS Center, St. Petersburg City AIDS Center) and addiction hospitals (Leningrad Regional Center for Addictions, St. Petersburg City Addiction Hospital) through notification of patients and providers at these sites. At each

of the recruitment sites flyers with information about the trial will be distributed to clinicians and peers working with HIV-positive patients. Flyers will provide a phone number (at Pavlov) for interested individuals to call to find out more about the study and undergo initial screening over the phone. On occasion, Pavlov research assessors may travel to screen participants at the affiliated clinical locations.

4.2 SCREENING

Screening may take place over the phone or in-person. Verbal consent for screening will be obtained from all potential participants. Potential participants will be asked by a research assessor, either on the phone or in-person, their age, HIV infection status, past year alcohol consumption, chronic pain, and pregnancy status, confirm residence within 100km of St. Petersburg, and possession of a phone, and two contacts to assist with follow-up, and ability and willingness to comply with all study protocols and procedures. If the participant is not fluent in Russian, has a cognitive impairment resulting in inability to provide informed consent, reports breastfeeding, has known uncontrolled psychiatric illness (such as active psychosis), has known active tuberculosis or current febrile illness, has a history of hypersensitivity to naltrexone, nalmefene, or naloxone, has known liver failure, has a history of Reynaud's disease, has ALT/AST levels $>5x$ ULN, is currently using (past week) illicit or prescribed opiates, is unwilling to abstain from opiates in during the treatment period, is currently using psychotropic or neuroleptic medications or has a history of seizure disorder, has any planned surgeries in the next three months, if the participant is enrolled in another HIV and/or substance use intervention study, or has taken naltrexone or nalmefene in the past 30 days then s/he will be deemed ineligible. We will also collect information on participants' average pain in the past week, pain interference with their enjoyment of life in the past week, and pain interference with their general activity in the past week. These data will be used to describe the sample, including those individuals who screen ineligible, but will not be used for assessing eligibility. After informed consent is signed, a confirmatory pregnancy test will be done for all female participants and urine drug test for all. Rapid HIV testing will be conducted, via an Alere Determine™ HIV-1/2 visual read, qualitative immunoassay for the detection of HIV-1 and HIV-2 antibodies, for all non-Russia ARCH/St PETER participants. Participants have the option of bringing in a recent (must be dated within 4 weeks of the screening visit) liver function test result to the screening visit to assess for eligibility, all other participants will have their blood drawn and sent for AST/ALT testing. Data collected on participants who screen out will be kept in order to have an accurate record of the rate of enrollment among those screened for participation and to be able to identify reasons why potential participants are ineligible. The data will not contain identifying information.

If a participant is screened over the phone, the participant will be re-screened in-person.

Participants' screening IDs will be linked to their subject ID in an Excel spreadsheet. A separate Excel spreadsheet will link participants' ID numbers to their contact information.

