- 6) Severe hepatotoxicity: we will test aminotransferase levels (AST/ALT) at baseline and at 4 and 8 weeks to look for severe hepatotoxicity defined as $AST/ALT > 10X$ the level of normal. Hepatotoxicity rarely occurs in the setting of treatment with naltrexone among persons with HIV;¹ less is known of the safety of nalmefene among persons with HIV, however hepatotoxicity is not listed as an adverse event in the product insert. This threshold was selected as it is 10X upper limit of normal (ULN) recognizing that the population with alcohol use and commonly hepatitis C may start off with AST and ALT above the ULN. Any elevation in AST/ALT beyond ULN will be evaluated by the investigators as a potential adverse event: if elevations are felt to be dangerous/life-threatening medications may be stopped at an even lower threshold. We consulted with experts in the field, with one (Yale Professor of Medicine, NIDA researcher who has done research involving Naltrexone) noting that "Grade 4 (10x) is the standard for STOPPING and monitoring for all of these trials UNLESS there is a clear indication that toxicity is a major concern (which it is not here based on a large amount of literature)."² (Springer et al., 2012)

[figure not shown]
For feasibility, descriptive purposes, and to refine our measurements, we will also assess pain (self-reported and experimental) at baseline, week 4 and week 8.

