2.3 STUDY DESIGN

This is a randomized, double-blinded, 2-arm study of 16 participants with HIV, chronic pain (defined as any bodily pain of moderate to severe intensity lasting for ≥ 3 months), and past-year heavy alcohol use, defined by NIAAA criteria. The 16 participants will be randomly assigned to either naltrexone or nalmefene with a 1:1 allocation ratio using permuted blocks to ensure equal numbers in each arm. Although we will not be formally testing differences between the naltrexone and nalmefene groups, participants will be randomized to the 2 arms in order to minimize selection bias and confounding in the allocation of interventions. Participants will be treated for 8 weeks, and outcomes (tolerability, alcohol use, side effects, medication adherence and discontinuation, and willingness/desire to continue to take medication at the end of study) will be evaluated at the end of treatment. In addition, we will review changes in pain during treatment with naltrexone and nalmefene to ensure that pain does not get worse and determine whether there is some improvement.

The study design and schedule for study visits and assessments is depicted in Figure 1. After consent and enrollment participants will be randomly assigned to either low-dose naltrexone or standard-dose nalmefene. The schedule of study in-person visits/assessments are as follows: screening visit, baseline, 2, 4, 6, and 8 weeks. At baseline, weeks 4 and 8, full study visits will occur, including assessments of tolerability of medication, medication discontinuation, treatment side effects, self-reported adherence and confirmation of adherence through riboflavin urine testing, self-reported pain, and experimental cold pain tolerance (cold-pressor test). Participants will also be instructed to keep a daily dairy to record pain severity, medication adherence, and alcohol use. Weeks 2 and 6 will be short visits at which time a brief assessment of tolerability, side effects, and adherence will occur. Throughout the course of the study, participants will be expected to come in for three in-person assessments and blood draw visits (screening/baseline, 4- and 8-weeks) and two shorter in-person visits.

Figure 1: Study Design (UH2 Phase)

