3. INTERVENTION

3.1 INTERVENTION OVERVIEW

The study will randomize 16 HIV+ persons with past year heavy alcohol consumption (by NIAAA definition of at risk drinking) and chronic pain (defined as bodily pain of moderate to severe intensity lasting for ≥ 3 months). Existing Russia ARCH participants will be offered to be screened for this study. Recruitment beyond First St. Petersburg Pavlov State Medical University (PSMU) will occur at local NGOs, Russia ARCH network hospitals including the major clinical HIV and addiction hospitals. Some participants may be screened over the phone, but all interested potential study participants will ultimately be invited for an in-person screening of eligibility at PSMU. After eligible participants are consented and enrolled, the RA will complete screening for eligibility by conducting a rapid HIV test for non-ARCH participants, a urine drug test, and blood draw for AST/ALT testing and testing all women for pregnancy (urine). Once AST/ALT results are received, participants will be notified by phone and if eligible, will be invited to return to Pavlov for their baseline visit.

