If the participant fails the naloxone challenge, s/he will be invited to come back within a week to repeat the challenge. Participants who pass the naloxone challenge will then complete the study assessment, cold-pressor testing and be randomly assigned to either low-dose naltrexone or standard-dose nalmefene. Study medication will be provided by trained physicians, who will instruct participants in proper medication administration and adherence.

Study participants, investigators, staff, and physicians administering the medications will be unaware of specific group assignment.

Participants will be treated for 8 weeks, and outcomes (alcohol reduction, tolerability, side effects, medication adherence and discontinuation, and willingness/desire to continue to take medication at the end of the study) will be evaluated at the end of treatment.

Throughout the course of the study, participants will be expected to come in for five in-person assessments. The schedule of study in-person visits/assessments are as follows: baseline, 2, 4, 6, and 8 weeks. At weeks 4 and 8, full study visits will occur, including assessments of tolerability of medication, reduction in alcohol use, medication discontinuation, treatment side effects, self-reported pain, and experimental cold pain tolerance (cold-pressor test). Participants will also be instructed to keep a daily diary to record pain severity, alcohol use, and medication adherence. Weeks 2 and 6 will be short visits, at which a brief assessment of tolerability, side effects, and adherence will occur.

Visits will be preceded by phone/text reminders to the participant or alternate contacts.

The text message will read: "This is a reminder that your visit to Pavlov Medical University is scheduled for ____ at _____. Please reply to confirm or call [name] to reschedule."

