3.3 INTERVENTION

As of September 18th, 2018, enrollment into arm A of the study was discontinued due to concerns about tolerability of the medication. Enrollment into arm B of the study will continue until we reach the target sample size for this arm (N=8).

Eligible participants will be randomly assigned into one of two study arms: 1) 4.5 mg naltrexone or 2) 18mg nalmefene. Study medication will be provided by trained physicians, who will instruct participants in proper medication administration and adherence.

Drug capsules containing naltrexone hydrochloride (4.5mg) and nalmefene hydrochloride dihydrate (18mg) will be prepared by NonStopPharma, a compounding pharmacy in St. Petersburg, Russia. Doses will look identical; participants and providers will be blinded to assigned medication. Both medication capsules will include Riboflavin. Participants will be instructed to take one capsule orally once per day for 8 weeks. Participants will be given 28 days' worth of medications, with instructions to bring pill bottles/leftover medications to the following visit. Although medication visits will occur every two weeks, providing participants with 28 days of medications will ensure that they will not run out even if they miss the 2 and 6 week visits.

The Food and Drug Administration (FDA) has indicated that an Investigational New Drug (IND) is not needed for studies conducted outside the United States.

3.3.A. NALTREXONE

Participants randomized to this group will receive low-dose naltrexone for 8 weeks.

Participants will be instructed to take the medication once daily for 8 weeks. Naltrexone dosing will start on the day of the baseline visit, after successful passing of the naloxone challenge. If the participant does not pass the naloxone challenge, they will be brought back within a week to try again.

The most common side effects (reported in more than 1 in 10 people) of naltrexone are difficulty sleeping, anxiety, nervousness, abdominal pain/cramps, nausea and/or vomiting, low energy, joint and muscle pain, and headache.

Uncommon side effects (reported in less than 1 in 10 people, but more than 1 in 100 people) of naltrexone are loss of appetite, diarrhea, constipation, increased thirst, increased energy, feeling down, irritability, dizziness, skin rash, delayed ejaculation, decreased potency, and chills.

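### The 4-week age limit on an outside AST/ALT result runs to screening, not to first dose, so the value behind the >5x exclusion can be 31 days old at the target date and 56 days at an in-window baseline visit (minor, safety only)

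*Combined protocol and SAP*

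**What the plan says.** Section 2.6 excludes anyone with "ALT/AST levels >5x normal". Section 4.2 gives two ways to supply the value at screening. The participant may bring "a recent (must be dated within 4 weeks of the screening visit) liver function test result", or blood is drawn by the study. Section 4.4 repeats that the draw is made only when no recent result is supplied. Section 3.1 settles eligibility before the next visit: "Once AST/ALT results are received, participants will be notified by phone and if eligible, will be invited to return to Pavlov".

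Section 3.5.A opens the baseline window 1 day after screening, sets the target at 3 days and closes the window at 28 days. Sections 3.3.A and 3.3.B start dosing on the baseline day once the naloxone challenge is passed.

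The AST/ALT row in 3.5 marks screening, week 4, week 6 if indicated, and week 8. Section 3.6.C agrees, and the baseline list in 4.4 has no blood draw. Two places are worded differently. Section 2.2 says "we will test aminotransferase levels (AST/ALT) at baseline and at 4 and 8 weeks", and Section 2.3 counts "three in-person assessments and blood draw visits (screening/baseline, 4- and 8-weeks") among the in-person visits. Neither limits the age of the value at first dose or holds dosing for a result.

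**The concern.** The >5x exclusion is the only AST/ALT check before dosing. The participants drink heavily, and Section 2.2 expects that some will start above the upper limit of normal. By setting a 4-week limit, the protocol shows that it wants a fairly recent value, but the limit stops at screening and the screening-to-baseline interval is added on top. For people who bring an outside result, nothing then bounds the age of the value at 4 weeks when the first capsule is taken. Pregnancy and urine drug tests, by contrast, are repeated at the baseline visit.

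What is at stake is how current one safety check is. Section 2.2 concedes that "less is known of the safety of nalmefene among persons with HIV". The next scheduled AST/ALT after first dose is week 4, whose window runs from day 21 to day 34.

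**Working it through.** Inputs:
- Age limit for an outside result at screening: 4 weeks = 28 days (4.2).
- Age of a study draw at screening: 0 days (4.2, 4.4).
- Screening to baseline: 1 day at opening, 3 at target, 28 at close (3.5.A).
- First dose: the baseline day (3.3.A, 3.3.B).
- Repeat naloxone challenge: up to 7 days later (3.1).

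The protocol's own figure first: baseline window length = close − open = 28 − 1 = 27 days, as stated in 3.5.A. The protocol gives no figure for the age of AST/ALT at first dose.

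Age at the baseline visit = age at screening + days from screening to baseline.

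| Route | Window opens | Target date | Window closes |
|---|---|---|---|
| Study draw | 0 + 1 = 1 | 0 + 3 = 3 | 0 + 28 = 28 |
| Outside result at its limit | 28 + 1 = 29 | 28 + 3 = 31 | 28 + 28 = 56 |

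The excess over a 28-day limit counted to baseline is 31 − 28 = 3 days at the target date and 56 − 28 = 28 days at window close.

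The table takes the first naloxone challenge as passed. After a failed challenge, "s/he will be invited to come back within a week to repeat the challenge". The protocol does not say whether that return must fall inside the baseline window. If it may fall outside, the maximum age at first dose becomes 28 + 7 = 35 days for a study draw and 56 + 7 = 63 days for an outside result.

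Reach of the proposed rule: with baseline booked on day d, an outside result aged a days at screening needs a study draw when a > 28 − d. Of the 29 whole-day ages (0 to 28) now accepted:
- d = 3: a = 26 to 28 (3 ages)
- d = 14: a = 15 to 28 (14 ages)
- d = 28: a = 1 to 28 (28 ages)

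A draw taken at screening is at most 28 days old throughout the baseline window.

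**The case against.** The rule is clear, Sections 4.2 and 4.4 apply it in the same way, and nothing in the protocol requires AST/ALT within 28 days of dosing. That stands: this is an improvement to a design choice, not an error or a contradiction.

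The protocol also tolerates values above 5x once treatment has begun. Section 3.4.E stops medication at week 4 only above 10x; between 5x and 10x the participant stays on drug and is rechecked at week 6, although 2.2 allows earlier stopping on the investigators' judgement. Drifting past 5x before first dose would thus put a participant in a range that the protocol accepts under treatment. Section 2.2 argues that liver risk is low: hepatotoxicity is rare with naltrexone in HIV and is not listed in the nalmefene insert. The known-liver-failure exclusion, two-weekly symptom review and symptom-triggered AST/ALT testing add protection. All of this stands and keeps the point minor.

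The 56 days is a joint extreme: a result at its age limit and a visit on the last permitted day. At the target date the excess is at most 3 days. That stands too.

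A reader might infer from the baseline wording in 2.2 and 2.3, the undefined clinical-values row marked at baseline in 3.5, and the mention in 6.2 of abnormal laboratory results from that visit, that a fresh AST/ALT is available at dosing. The documents do not support this. The separate AST/ALT row, 3.6.C and 4.4 place none there, and eligibility on AST/ALT is decided before the participant is invited to baseline.

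**Conclusion.** The point holds as a cheap, minor safety improvement. The value behind the >5x exclusion can be up to 31 days old at the target date and 56 days at an in-window baseline visit, against 3 and 28 days for a study draw, provided the first naloxone challenge is passed. Counting the limit to baseline would remove at most 3 days at the target date and at most 28 at window close.

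Few people can be affected. Section 3.3 closed arm A and states "Enrollment into arm B of the study will continue until we reach the target sample size for this arm (N=8"). The documents do not say how many participants bring an outside result, or which drug arm B is.

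A reader might infer that participants above 5x are being dosed, or that the hepatotoxicity outcome is compromised. The documents support neither. They give no information on how AST/ALT moves over these weeks. The outcome and the stopping rule are fixed on-treatment thresholds (>10x) that do not use the baseline value, and the >5x recheck at week 4 is equally untouched. The tolerability outcome, sample size and go/no-go rule are not involved.

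**What to change.** In 4.2 and 4.4, accept an outside result only if it will be no more than 28 days old on the scheduled baseline date; otherwise take the standard study draw at screening. If the visit is then rescheduled so that an accepted outside result is more than 28 days old, draw AST/ALT and apply the >5x exclusion before dosing. Limit this repeat to outside results, so that study draws keep their current rule. For consistency, mark the repeat as conditional in 3.5 and 3.6.C, as is already done for week 6. State in 2.2 that the latest pre-dose value is the baseline AST/ALT, which also reconciles 2.2 with 3.5.

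The sponsor should say whether a return for a repeat naloxone challenge counts as rescheduling. If it does not, an accepted outside result could reach 28 + 7 = 35 days at first dose, the same as a study draw.

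The cost is some wording and an extra draw at screening for some participants with an outside result: only those with results aged 26 to 28 days if baseline is booked on day 3, but more if it is booked later. Rarely, when a visit slips, first dose would be delayed and an extra trip might be needed, because AST/ALT results come back after the visit.
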